A docu-drama group of purposively selected 10 first-time donors will be formed. They will attend one meeting to watch two docu-dramas, each lasting 15 minutes, followed by a one-hour focus group discussion on the content of the drama, and feasibility, acceptability and cultural appropriateness of the intervention. Prior to, and after the viewing and discussion, a pre-, and post-test survey on the theory of planned behaviour constructs and implementation research measures will be conducted. Two study team members will facilitate the discussions. The docu-drama test-run will include an attendance list at the scheduled meeting. Those who attended, watch the 2 episodes, and stayed for the discussion will be considered as having adhered to the intervention.

The PROCEED Component will be addressed during the four years of the UH3 phase.

The PROCEED component involves exposing the interventions to participants and evaluating their outcomes. The UG3 pilot RCT will address the feasibility and inform the design of the PROCEED component.

The Theory of Planned Behaviour

As shown in Figure 4, according to the theory of planned behaviour, behavioural intention to return to donate in 6 months is influenced by factors such as attitude, subject norms, and perceived behavioural control, and has been examined in first-time blood donors (Masser et al., 2012). The theory of planned behaviour model will be used to evaluate the effect of intervention-specific changes in attitude, subject norms, and perceived behavioural control on intention to return to donate blood, and on actual return donation attempt.

[figure not shown]

Figure 3: Theory of planned behaviour

The Technology Acceptance Model

As shown in Figure 5, according to the technology acceptance model, intention to use technology (in this case, WhatsApp) is influenced by perceived usefulness and perceived ease of use of the technology (Venkatesh & Bala, 2008).

[figure not shown]

Figure 4: Technology Acceptance Model

Randomization

The docu-drama design and test-run will not employ randomization. The participants enrolled in the pilot RCT will be randomized immediately following the baseline assessment with a 1:1 allocation ratio to WhatsApp or control using blocked randomization (with randomly mixed

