WhatsApp: Participants assigned to the WhatsApp group will receive weekly messages developed by communication specialists aimed to motivate blood donation, be encouraged to discuss their blood donation experiences, and share their own motivations for donating blood in a moderated, closed group over a six-month duration. The moderator will provide guidelines on acceptable use of WhatsApp, including images they can or cannot share. Participants also receive standard NBSG communications for first-time donors (see below). WhatsApp functions both online and offline. When a participant's WhatsApp is offline (i.e. not connected to the internet), the participant can access posted messages received earlier, respond to these posts and post new comments. However, the participant can only receive newly posted messages only when the WhatsApp is connected to the internet (online). Similarly, the participant's posted messages will only be sent when the participant's WhatsApp is back online.

Control: Participants in this group will receive the standard NBSG communications for first-time donors 1) a “thank you” phone call and 2) and a reminder phone call two-weeks prior to the second blood donation eligibility. The second blood donation eligibility is four months after the first donation.

Avoiding intervention contamination: For the docu-drama intervention, only those invited to receive the intervention will be allowed to view the docu-drama in and be part of the discussions to avoid intervention contamination. In addition, the docu-drama viewing will be conducted face-to-face, which will make it impossible for those who are not present to share the content. For the WhatsApp intervention, only those randomly selected to be part of the WhatsApp intervention group would receive the messages and be part of the discussion. Participants will be advised against sharing the contents of the WhatsApp intervention with those who are not in the group to avoid contamination.

As shown in Figure 2, the two interventions, WhatsApp and docu-drama, are expected to lead to sharing of positive experiences, leading to repeat blood donors. However, for these to occur, the project has several assumptions as indicated in black triangles.

[figure not shown]

Figure 5: The Theory of Change: Community-Based Communication Approaches for Blood Donation in Ghana

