A major assumption is that there will be high fidelity of the interventions. We will assess adherence to the interventions as a key element of fidelity (Carroll et al., 2007). Adherence will include subcategories of content, frequency, duration and dose (Carroll et al., 2007). The extent to which the intended content or frequency of WhatsApp and docu-drama are implemented will

represent the degree of implementation fidelity achieved for the two interventions (Carroll et al., 2007; Song et al., 2010).

Study Population

Inclusion Criteria

Docu-drama design

Design workshop participants will be drawn from blood donors, non-blood donors, drama experts, drama actors, and communication professionals. All must be at least 18 years old, consent to participate and understand English.

WhatsApp intervention design

Key informants will be drawn from the NBSG staff, community-based blood donation volunteers, blood donors, and non-blood donors. All must be at least 18 years old, consent to participate, and understand one of English, Twi, or Ga.

Pilot RCT

- At least 18 years-old
- First-time whole blood donor with the SZBC of the NBSG
- Eligible to donate again
- Consent to participate
- Understands one of English, Twi, or Ga
- Have a smart phone
- Have, or be willing to sign up for an active WhatsApp account

Docu-drama test-run

- At least 18 years-old
- First-time whole blood donor with the SZBC of the NBSG
- Eligible to donate again
- Consent to participate
- Understands one of English, Twi, or Ga

Exclusion Criteria

Docu-drama design

Do not meet the above inclusion criteria

WhatsApp intervention design

Do not meet the above inclusion criteria

Pilot RCT

History of more than one lifetime whole blood donation (with any blood centre)

Docu-drama test-run

History of more than one lifetime whole blood donation (with any blood centre)

Outcome measures

Primary Outcome

The primary outcome for the pilot RCT is to estimate the proportion of return blood donation attempts within six months of enrollment for each arm.

Secondary Outcomes

The secondary outcomes are the following measures.

WhatsApp and control

- Blood donation attitudes,
- subjective norms,
- perceived behavioural control,
- intention,
- ease of use of WhatsApp,
- perceived usefulness of WhatsApp.

Docu-drama, WhatsApp and control

- Intention of using the intervention

- Acceptability of the intervention
- Feasibility of the intervention
- Cultural appropriateness of the intervention

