The participants will be invited to participate in screening after blood donation at SZBC sites.

Table 1: Schedule of assessments for pilot RCT

Assessment	Screening (At first-time donation)	Baseline A pre- randomization (Day 0)	Baseline B post- randomization (Day 0)	6-month follow-up (Days 176- 190) ¹	6-12 months follow-up
Informed Consent Form	X				
Demographics	X				
Blood donation attitudes, subjective norms, perceived behavioural control, and intention		X		X	
Randomization			X		
Intention of using the intervention			X		
Acceptability of the intervention			X	X	
Feasibility of the intervention			X	X	
Cultural appropriateness of the intervention			X	X	
Perceived usefulness of the intervention			X	X	
Perceived ease of use of the intervention			X	X	
Intervention relatedness			X	X	
Return blood donation attempts ²				X	
Focus groups of participant views of acceptability, effectiveness, feasibility, and cultural appropriateness					X
Note: The participants involved in the test-run of the docu-drama will be surveyed prior-to and after the docu-drama with all instruments (except blood donation attempts) and participate in facilitator-led focus groups.					
¹ 6-months with a 2-week window.					
² Donor return will be assessed via telephone calls and cross-checked with SZBC donor records.					

Follow-up assessments for the pilot RCT

There will be two follow-up assessments.

6 months

The 6-month assessment for the pilot RCT will occur over the phone with a 2-week window of the 6-month pilot. Donor return will be assessed via telephone calls and cross-checked with SZBC donor records. The six-month follow-up will repeat baseline post-randomization questionnaires and include the intention of using the intervention, acceptability of the intervention, feasibility of the intervention, cultural appropriateness of the intervention, perceived ease of use of the intervention, perceived usefulness of the intervention, and intervention relatedness. In line with definitions of acceptability, appropriateness and feasibility given by Weiner et al. (2017), we defined these characteristics as follows:

Acceptability is the perception among first-time blood donors that an intervention is agreeable or satisfactory for promoting blood donation. Thus, acceptability will be measured with a five-item questionnaire.

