Below are a number of statements relating to the participant's intent to donate blood. Read each statement to the participant, and have them indicate where they fall on the scale from 1 to 5.

1. I plan to donate blood in the next 4 months

Strongly Disagree 1 2 3 4 5 Strongly Agree

2. How likely is it that you will donate blood in the next 4 months?

Very Unlikely 1 2 3 4 5 Very Likely

3. I will donate blood in the next 4 months.

[figure not shown]
Very Unlikely 1 2 3 4 5 Very Likely

Signature: _____

Date: _____

7. Case Report Form for participants enrolled in the RCT of the study after randomization

[figure not shown]
Baseline B

Participant ID:	Form Date: (example: 01-APR-2021)	Participant 3-letter code:	Bloodsafe Logo Placeholder
	Form Date: (example: 01-APR-2021)  Day Month Year	Participant 3-letter code: 	Site: 01 Korle-Bu Bld Bank 02 Korle-Bu Maternity 03 Pentecost Hospital 04 LEKMA Hospital 05 Maamobi Polyclinic 06 Accra Shopping Mall 07 Mobile Unit

Complete this form immediately after randomization for all participants enrolled in the RCT of the C-CAD study.

A. Randomization

(example: 01-APR-2021)

1. Date of participant randomization: 

2. Indicate which arm of the study the participant is in. Follow the instructions listed for the arm.

- 1 Control
 2 WhatsApp

B. Intention of Using the Intervention

Yes No I don't know

1. I intend to use WhatsApp to discuss blood donation in the next 6 months

1 0 2

2. I intend to use WhatsApp to discuss blood donation as often as possible

1 0 2

3. I expect my use of WhatsApp to discuss blood donation to continue in the future

1 0 2

Items C, D, and E have a number of statements related to the acceptability, feasibility, and cultural appropriateness related to potential use of WhatsApp for blood donation education. Read each statement to the participant, and ask them to respond "Yes", "No", or "I don't know" to each statement.

C. Acceptability

Yes No I don't know

1. Using WhatsApp for promoting blood donation among first-time donors **is appealing**

1 0 2

2. Using WhatsApp for promoting blood donation among first-time donors **seems fine with me**

1 0 2

3. I have **no objection** to using WhatsApp for promoting blood donation among first-time donors

1 0 2

D. Feasibility

Yes No I don't know

1. Using WhatsApp for promoting blood donation among first-time donors seems **practical**

1 0 2

2. Using WhatsApp for promoting blood donation among first-time donors seems **possible**

1 0 2

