E. Demographics (continued)

12. What is your ethnic background?

- 1 Akan
- 2 Ewe
- 3 Dagbani
- 4 Ga/Dangbe
- 5 Hausa
- 6 Other, specify: _____

13. Do you belong to a religious faith?

- 1 Yes, Christian
- 2 Yes, Moslem
- 3 Yes, Traditionalist
- 4 Yes, Other, specify: _____
- 5 No

Signature: _____ Date: _____

16. Participation Withdrawal Form

Withdrawal

Participant ID:

Date of withdrawal:

(example: 01-APR-2021)

- - 0 2

Day

Month

Year

Participant
3-letter code:

Bloodsafe Logo
Placeholder

Site:

01 Korle-Bu Bld Bank
02 Korle-Bu Maternity
03 Pentecost Hospital
04 LEKMA Hospital
05 Maamobi Polyclinic
06 Accra Shopping Mall
07 Mobile Unit

Complete this form if a participant has actively (verbally or in writing) withdrawn consent or if the participant is withdrawn by the PI from the C-CAD study.

A. Withdrawal

1. Indicate the type of withdrawal (mark only one):

- 1 Participant actively withdrew consent from all aspects of the C-CAD study
2 Administrative withdrawal

2. The participant requested destruction of the following (mark all that apply):

- 1 All participant recordings
2 All participant data
3 N/A (The participant did not request destruction of data or recordings)

3. Reason for withdrawal:

- 1 Participant preference
2 Staff/PI request
3 IRB/sponsor request
4 Other; specify: _____

Staff person completing this form (please print): _____

Signature: _____

Signature indicates a withdrawal has been verified with site and all necessary documentation is available.

17. SOP: Randomizing participants into study groups for the pilot RCT of WhatsApp and control

BLOODSAFE: Standard Operating Procedure

Randomizing participants into study groups for the pilot RCT of WhatsApp and control		Version 0.3 15 Feb 2021
---	--	-----------------------------------

Revision history		
Version	Date	Description

1. Purpose

The purpose of this standard operating procedure (SOP) is to describe how to use the randomization application for the pilot RCT of WhatsApp and control for the *Community-Based Communication Approaches for Blood Donation in Ghana-Pilot Study* (C-CAD) study. Participants are allocated with a 1:1 ratio to WhatsApp or control stratified by one of two donor types (e.g., Voluntary non-remunerated donor or Family/replacement donor) using the web-based application described in this SOP. Participants will be randomized after the consent and screening process immediately following completion of Baseline A case report form (CRF).

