2. Scope and responsibilities

Allocation into study groups for C-CAD will be performed using the randomization application tool on the study website. The protocol principal investigator determines who will be given randomization privileges. Only the research assistants (RAs) assigned to C-CAD randomization as listed in the delegation log for this protocol will have access to the randomization application tool. The web-based application has been designed so that the upcoming intervention assignment is concealed from the study staff prior to the randomization outcome.

[figure not shown]
3. Accessing the randomization application on the website.

Only study RAs with randomization permissions for C-CAD will be able to see the link for the randomization application tool. Each study RA with permissions must complete the training requirements prior to randomizing a C-CAD participant. Training includes at least 3 practice randomizations using a test website and the training must be documented by the data coordinating center.

The randomization application tool, [Randomization Application \(Pilot RCT of WhatsApp and Control\)](#), is located under the C-CAD specific protocol page below [Documents and Downloads](#) (see Figure 1). If you do not see the randomization application, you do not have permissions to randomize participants for C-CAD.

BLOODSAFE: Standard Operating Procedure

Randomizing participants into study groups for the pilot RCT of WhatsApp and control		Version 0.3 15 Feb 2021
--	--	----------------------------

The screenshot shows the BLOODSAFE website interface. On the left, a sidebar lists 'Research Projects in' with 'Ghana' selected, which is highlighted with a red circle. Under 'Ghana', the 'C-CAD' button is also highlighted with a red circle. The main content area is titled 'Ghana: C-CAD' and describes a pilot randomized controlled trial for increasing the blood donor pool in Ghana. It includes details about the study design, principal investigators, and Clinicaltrials.gov identifier. Below this, a 'Documents and Downloads' section is shown, with the 'Randomization Application (Pilot RCT of WhatsApp and Control)' link highlighted with a red circle.

Figure 1: Location of randomization application on the BLOODSAFE website.

4. Performing individual random group allocation during an onsite blood donation visit.

4.1. Determine the type of donor for this blood donation visit using the study definitions.

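### The baseline intention and control items ask about a four-month period that ends about when second-donation eligibility begins, while the plan frames intention and outcome at six months; one norm item says weeks where the others say months

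*Combined protocol and SAP*

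**What the plan says.** - **Item wording.** Baseline A, section G (Blood Donation Intention) opens with "I plan to donate blood in the next 4 months". The other two intention items, all five control items (section F), the stem of the six attitude items (section D) and norm items 1 to 5 (section E) also look four months ahead. Norm item 6 looks four weeks ahead. The Month 6 form and the post-viewing docu-drama form repeat this wording, including the four-week item.
- **Timing of the form.** Under Schedule of Assessments, "The participants will be invited to participate in screening after blood donation at SZBC sites". Table 1 puts Baseline A on Day 0. The randomization SOP has participants randomized straight after Baseline A, and its section 4 is titled "Performing individual random group allocation during an onsite blood donation visit".
- **Eligibility.** Study Interventions, Control: "The second blood donation eligibility is four months after the first donation".
- **Intended construct.** The Theory of Planned Behaviour section says that "behavioural intention to return to donate in 6 months is influenced by factors such as attitude, subject norms, and perceived behavioural control". It plans to study, by intervention, the influence of "changes in attitude, subject norms, and perceived behavioural control on intention to return to donate blood, and on actual return donation attempt".
- **Outcome window.** The primary outcome is "the proportion of return blood donation attempts within six months of enrollment for each arm". Section P of the Month 6 form looks back over six months and also records attempts that failed donor screening.

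No section explains the four-month horizon or the four-week item.

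**The concern.** A donor who knows the interval and plans to come back in month 5 could truthfully give low answers to the baseline intention and control items, and then count as a return. The baseline score would reflect the calendar rather than the donor's disposition.

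Attitude, norms, control and intention are listed as secondary outcomes, and the plan means to relate changes in them to return attempts. For a participant who has not donated again, the same words at Month 6 describe a fully eligible period. Part of any change between visits could therefore reflect eligibility. The pilot is meant to inform the UH3 trial, so an instrument left as it is may be carried forward.

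The four-week item raises a separate matter: it mixes two horizons in one six-item scale.

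**Working it through.** The plan gives no figure on this point, so the check is item counting and calendar arithmetic.

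**Inputs.** Eligibility at 4 months after the first donation (Study Interventions, Control); item horizon 4 months (Baseline A, sections D to G); outcome window 6 months from enrollment (Primary Outcome); Day 0 at the donation visit (Table 1, randomization SOP).

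**Items.** Four-month wording: attitude 6 + norms 5 + control 5 + intention 3 = 19 of 20. Four-week wording: 1 of 20 (norm item 6). Control and intention together: 5 + 3 = 8.

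**Days, with a month of 365.25/12 = 30.44 days.**
- Eligibility starts: 4 × 30.44 = day 121.75 (120 to 123 by calendar month).
- Outcome window ends: 6 × 30.44 = day 182.6 (181 to 184).
- Eligible days inside the outcome window: 182.6 − 121.75 = 60.9, about 61 (59 to 62).
- Eligible days inside the baseline item horizon: 121.75 − 121.75 = 0.

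**Sensitivity.**
- Length of a month: with eligibility at 112 days (28-day months) and the item horizon at 123 days, the overlap is 123 − 112 = 11 days, or 11/123 = 9% of the horizon.
- Lag (an assumption): if Baseline A follows the donation by L days, the items cover L eligible days. The outcome window, counted from enrollment, then holds 60.9 + L. For L = 7 that is 7 of 67.9 days (10%); for L = 14, 14 of 74.9 days (19%).

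**What six-month wording would do.** At baseline, 60.9/182.6 = 33% of the item horizon would be eligible time, against 0% now. At Month 6, a participant who has not donated again is eligible throughout under either wording. The difference between visits shrinks but remains. These are shares of calendar time, not of any score.

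**Month 6 for those who returned.** Assume the same interval applies after a second donation and the visit falls at day 182.6. A donor who returned on day 121.75 is eligible again at day 243.5. The four-month horizon ends at 182.6 + 121.75 = day 304.4, so (304.4 − 243.5)/121.75 = 50% of it is eligible. A donor who returned on day 182.6 is eligible again at day 304.4, so the share is 0%. Non-returners have 100%.

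**The case against.** The strongest reply is that four months is a spoken phrase on a five-point scale, not a day count. It equals the donation interval and may have been meant as the donor's next opportunity. The documents neither say so nor exclude it, so they support asking for reconciliation and do not prove a drafting error.

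Several further points stand and limit the concern:

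- **Attempts are not eligible donations.** A reader might infer that no return could count in the first four months. That does not follow: the outcome counts attempts, the Month 6 form includes failed screening, and about 122 of the 183 days precede eligibility.
- **Same-day completion is likely but not certain.** Table 1 separates screening from Baseline A, and the COVID-19 section plans surveys by phone or online where possible. The SOP points to the donation visit; a short lag gives the small overlap shown above.
- **Reach.** Norm items 4 to 6 concern other people's donations, so the participant's eligibility is irrelevant there. Attitude items and norm items 1 to 3 are affected less directly. For the docu-drama test-run, time since first donation is not stated, so no eligibility mismatch is shown on that form.
- **Knowledge of the interval.** The Month 6 form offers not knowing when to return as a reason for not donating, so some donors may not answer with the interval in mind.
- **Internal match.** Apart from norm item 6, the predictors and intention share one horizon. The mismatch bears on their link to return attempts.

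On balance between arms, a reader might infer either that the wording favours an arm or that it is harmless throughout. Neither is shown. The baseline wording is common to both arms. At Month 6, participants who donated again in months 5 and 6 may be back inside the interval, so neutrality is not guaranteed if return differs by arm.

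**Conclusion.** The concern holds as a minor measurement point. The three intention and five control items on Baseline A cover about 0 of the roughly 61 days on which an eligible second donation can fall within the outcome window, or 7 to 14 days if a lag of one to two weeks is assumed. The attitude items and norm items 1 to 3 share the problem less directly. Norm item 6 is inconsistent with the rest of its scale on all three forms.

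This rests on the stated four-month eligibility, on Baseline A being completed at or near the first donation, and on eligible donations rather than attempts. The Month 6 remark also assumes that the interval applies after later donations.

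It is tempting to read the calendar shares as the size of a bias. The documents do not support that: they give no information on how donors interpret the items, and the effect on scores cannot be computed. The primary outcome and sample size are unaffected.

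**What to change.** Before first enrolment, and without taking a position on the donation interval:

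1. Reconcile the item horizon with the Theory of Planned Behaviour, Control and Primary Outcome sections by using the plan's own six-month horizon for these items on Baseline A and Month 6. Use the same wording on the post-viewing docu-drama form, for consistency only. Baseline B already asks about WhatsApp use over six months, so the horizon is workable.
2. Make norm item 6 match the other norm items on all three forms.
3. Add the reworded scales to the reliability assessment already planned under Secondary Objectives and Secondary Outcomes.
4. State that six months reduces, but does not remove, the difference in eligible time between visits.

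The cost is rewording three forms, including the Twi and Ga wording. The four scales become modified instruments and join the five measures already listed for reliability assessment. No new visits or data are needed. If enrolment has begun, keep the wording so that visits stay comparable, and state the limitation.

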2. Feasibility of recruitment, enrollment, retention and adherence with a two-arm pilot RCT (WhatsApp and control). A target retention rate of at least 90% completing the pilot trial is sought. Retention will be measured by the proportion of participants who will remain in the study by the end of the follow-up period. If we are unable to achieve this target, alternative strategies will be considered for the UH3 phase. One of the primary objectives is to estimate the proportion of successful return blood donation for planning the programmatic randomized clinical trial in the UH3 phase.
3. Acceptability will be assessed with quantitative surveys and participant focus groups to understand the opinions and perspectives of acceptability, effectiveness, feasibility and cultural appropriateness of the docu-drama, WhatsApp and control communication interventions.

Secondary Objectives

To design culturally appropriate communication interventions: docu-drama and WhatsApp groups for retaining first-time blood donors using the PRECEDE-PROCEED framework.

To examine intervention-specific increases in knowledge, attitudes, beliefs, motivations, intention, and relatedness as potential mediators of intention to donate among first-time blood donors. Evaluate the reliability of new or modified outcome measurement instruments.

Study Design

The pilot study utilizes a mixed-methods approach to develop a novel docu-drama communication strategy, evaluate the feasibility of a larger pragmatic randomized controlled trial (RCT) of a WhatsApp based communication strategy and assess acceptability of the communication strategy aimed to increase blood donation among first time blood donors within the catchment areas of the SZBC.

There are two communication interventions: docu-drama and WhatsApp. However, because the development of the docu-drama takes more time, it will not be feasible to include the docu-drama intervention in the pilot RCT, recruit 100% participants, follow up for 6-months for the primary outcome and evaluate the secondary outcomes, considering the duration the UG3 phase. Therefore, only the WhatsApp intervention will be piloted in the RCT. The docu-drama intervention will be designed and test-run in preparation for an RCT in the UH3 phase.

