We will consider factors that must be in place to initiate and sustain first time blood donors' attempts at returning to donate blood. These are called predisposing, enabling and reinforcing factors. We will identify these factors through analysis of primary and secondary data, and put them into categories, and rank their importance.

Predisposing factors, which explain first-time blood donors' behaviour regarding subsequent donation efforts, include knowledge, attitudes, cultural beliefs, and readiness to change. Enabling factors, which enable first-time blood donors to act on their beliefs, attitudes, and knowledge, include the availability of policies, assistance, or resources.

Reinforcing factors, which become prominent after a behaviour has been started, promote repetition or persistence of behaviour through the provision of continuing rewards or incentives such as praise or reassurance.

These factors will be identified from previous data on first-time blood donors in Ghana, and the key informant interviews with participants will be drawn from the NBSG staff, community-based blood donation volunteers, blood donors and non-blood donors.

Phase 5: Administrative and Policy Assessment

Identify the administrative and policy factors that influence what can be implemented. The team will evaluate how organizational factors such as policies, procedures, culture and the availability of resources influence what can be implemented by using two approaches to evaluate implementation research outcomes of the interventions. These are the creation of WhatsApp and docu-drama interventions and test-running the interventions.

WhatsApp pilot RCT

A WhatsApp group will be formed for the pilot RCT. There will be one study team member, who will be the content mediator (research assistant), and who will be responsible for sending

weekly messages and clarifications on blood donation for six months. The participants in the WhatsApp group, after the pilot RCT will have a focus group discussion on what worked well and what did not, and provide information on feasibility, acceptability and cultural appropriateness of the intervention. Prior to, and after exposure to the WhatsApp intervention, a pre-, and post-test survey on the theory of planned behaviour constructs and implementation research measures will be conducted.

Docu-drama test-run

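### Seven Baseline B scales, including donor relatedness, have no pre-randomization value, so change measured from Baseline B may carry an effect of knowing the arm

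*Combined protocol and SAP*

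**What the plan says.** Table 1 splits Day 0 into two forms. The row "Blood donation attitudes, subjective norms, perceived behavioural control, and intention" is marked before randomization. The rows for acceptability, feasibility, cultural appropriateness, usefulness, ease of use and relatedness are first marked in the post-randomization column and again at six months. Section 1 of the randomization SOP (study tool 17) places randomization directly after Baseline A.

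Baseline B (study tool 7) agrees with this: "Complete this form immediately after randomization for all participants enrolled in the RCT of the C-CAD study". Section A comes before any question to the participant and reads "Indicate which arm of the study the participant is in. Follow the instructions listed for the arm". The Blinding section says that participants are not blinded. It also says that baseline questionnaires are given by research assistants unaware of assignment.

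Two statements of purpose need a starting value. Under Secondary Objectives: "To examine intervention-specific increases in knowledge, attitudes, beliefs, motivations, intention, and relatedness as potential mediators of intention to donate among first-time blood donors". Under WhatsApp pilot RCT: "Prior to, and after exposure to the WhatsApp intervention, a pre-, and post-test survey", covering both the planned-behaviour constructs and the implementation research measures. For the implementation measures and relatedness, Baseline B is the only starting value collected.

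**The concern.** A variable measured after an unblinded allocation can be moved by that allocation. A participant just placed in a donor WhatsApp group may rate WhatsApp promotion more warmly, or feel more part of a donor community, than one just told they will receive standard communications only. If the arms separate at Baseline B for that reason, subtracting Baseline B or adjusting for it removes part of what is being measured.

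Relatedness is the measure to worry about most. The Rationale says that a WhatsApp intervention in Brazil used the platform for text messaging and did not assess it as a social-networking relatedness intervention. This pilot is meant to inform the larger UH3 trial on that mechanism, and a pre-randomization value that was never collected cannot be recovered later.

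**Working it through.** The plan gives no figure on this point, so the check is mainly one of order and coverage.

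**Order on Day 0.** Consent and screening, then Baseline A, then the randomization application, then Baseline B section A (date and arm), then Baseline B sections B to I. The weekly messages follow over six months.

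**Coverage, from the forms.**

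| Measure | First asked | Pre-randomization value? |
|---|---|---|
| Knowledge, beliefs | Baseline A, B and C | Yes |
| Attitudes, norms, control, donation intention | Baseline A, D to G | Yes |
| Intention of using the intervention (3 items) | Baseline B, B | No |
| Acceptability (3), feasibility (4), cultural appropriateness (3) | Baseline B, C to E | No |
| Usefulness (3), ease of use (3) | Baseline B, F and G | No |
| Donor relatedness (9), WhatsApp connectedness (12) | Baseline B, H and I | No |

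Sections C to I: 3 + 4 + 3 + 3 + 3 + 9 + 12 = 37 items. All are repeated on the Month 6 form.

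**Named mediators.** Of the six, knowledge, attitudes, beliefs and intention are on Baseline A. Motivations has no labelled scale on either form. Relatedness is the only one with a labelled scale that lacks a pre-randomization value.

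**Do the questions need the arm to be known?** The lead-in to C, D and E describes statements "related to potential use of WhatsApp for blood donation education". F and G ask about WhatsApp promotion and WhatsApp itself, H about other donors, and I about people on WhatsApp. None of this wording depends on assignment. Section B, on intention to use the intervention, is the only one where knowing the arm could be wanted.

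**How a shift would propagate.** Let learning the arm separate the arms by d SD at Baseline B, let rho be the correlation between Baseline B and Month 6, and assume equal SDs. The distortion is then:
- change-score contrast: d
- contrast adjusted for Baseline B: rho × d
- Month 6 contrast alone: 0

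If d has the same sign as the effect, the estimate is too small. A within-arm change in the WhatsApp arm is off by whatever shift occurred in that arm.

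**Illustration only.** The documents give neither d nor rho. For d from 0.1 to 0.5 and rho from 0.3 to 0.7, the distortion is 0.10 to 0.50 SD for change scores and 0.03 (0.3 × 0.1) to 0.35 (0.7 × 0.5) SD with adjustment. With the plan's effective 59 per arm, the standard errors in SD units are sqrt((2/59) × 2(1 − rho)) for change and sqrt((2/59)(1 − rho²)) with adjustment. At d = 0.3:

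| rho | Change: bias / SE | Adjusted: bias / SE |
|---|---|---|
| 0.3 | 0.30 / 0.218 = 1.4 | 0.09 / 0.176 = 0.5 |
| 0.5 | 0.30 / 0.184 = 1.6 | 0.15 / 0.159 = 0.9 |
| 0.7 | 0.30 / 0.143 = 2.1 | 0.21 / 0.131 = 1.6 |

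These SD units fit only the five-point items in F to I (3 + 3 + 9 + 12 = 27). The 10 items in C to E are answered Yes, No or I don't know, and no scoring rule is given for them.

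**The case against.** The defence has real substance. The protocol defines its pre-test relative to exposure, not allocation. Exposure means weekly messages and group discussion, and Baseline B comes before both. Table 1, the forms and the SOP show the same split, so it looks deliberate. The Quantitative Data Analysis section names generalized linear models for the secondary outcomes, with neither a change score nor a baseline covariate, and the randomized Month 6 contrast is valid whatever the timing of Baseline B. These are secondary outcomes in a pilot whose analysis is intentionally not focused on significance. Nor does any section say when participants are told their arm relative to answering.

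Most of this limits the point without removing it. A reader might infer that there is no unexposed baseline. That is wrong: the participants are unexposed, though probably not unaware of their arm. A reader might also infer that the mediator analyses in general lack a clean baseline. Four of the six named mediators have one, as do the norms and control measures used in the planned-behaviour change analysis.

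What remains is that an increase in relatedness and a pre/post survey on the implementation measures both imply some use of Baseline B, and no analysis is stated that avoids the problem. Early disclosure is an inference, but the lack of blinding and the position of the arm entry make it a strong one. The wording of C to I gives no reason for asking them late.

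**Conclusion.** The point holds in limited form. Seven scales (37 items) have no allocation-naive baseline. Two stated uses are exposed: the pre/post comparison on the implementation measures and the increase in relatedness. A distortion arises only if knowledge of the arm shifts the Baseline B answers and Baseline B is then used for change or adjustment. Its size is unknown, and the SD values above are assumptions, not estimates. The documents do not support saying that the pilot's mediator or acceptability results will be biased.

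The primary outcome, the Month 6 between-arm contrast, and the knowledge, beliefs, attitudes, norms, control and donation-intention measures are untouched. The change is worth making because it costs little and the missing value cannot be collected later.

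Separately, the Blinding statement that baseline questionnaires are given by assistants unaware of assignment does not fit a Baseline B form that records the arm before the questions.

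**What to change.** - Move sections C to I of Baseline B to the end of Baseline A, to be completed before the randomization application is opened.
- In Table 1, move the first mark in the six matching rows (acceptability, feasibility, cultural appropriateness, usefulness, ease of use, relatedness) to the pre-randomization column. Connectedness has no row of its own.
- Keep section A after randomization. Keep section B there too if intention given the assignment is wanted, and do not use it as a pre-randomization baseline.
- If the forms cannot be reordered, state in the analysis section that Baseline B will not be used for between-arm change scores or as a covariate, and rely on the Month 6 contrast.
- Reconcile the Blinding section with the arm entry on Baseline B, for example by stating who completes section A and who asks the questions.

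The reordering adds no items, visits or staff, and the SOP needs amending only if form names change. The cost is a longer form before randomization: a few donors may stop before being randomized. They would not enter the randomized comparison.
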